**Study start: July 15, 2019**

**Primary completion: July 19, 2019**

**Study completion: August 20, 2019**

### **Brief summary**

A retrospective consecutive population of patients treated with cementless total hip arthroplasty with ceramic-on-ceramic bearing surfaces due to post-traumatic osteoarthritis due to acetabular fractures will be selected. The aim of this retrospective study is to evaluate the long-term clinical and radiographic results of this implant in such a specific cohort. The secondary aim of the study is to provide the complication rate and the failure rate of the cohort. A descriptive analysis of the failures will be provided as well.

### **Study description**

Total hip arthroplasty (THA) is the recommended treatment to restore functionality and control pain in post-traumatic hip osteoarthritis due to acetabular fractures. However, THA in post-traumatic osteoarthritis following acetabular fractures is a complex procedure and it is burdened with occasional failures. Modest long-term outcomes have been reported, generally lower than conventional THAs performed due to osteonecrosis or primary osteoarthritis: 10-year clinical results are usually good but not excellent (average Harris Hip score: 88), 10-year revision rate is between 15% and 26%. In review study about the complications of post-traumatic THAs, 30% of ossifications, 4.4% of dislocations, 5.6% of infections, and 2.1% of neurovascular lesions were reported: all the percentages were higher than in primary conventional THAs.

The most critical issues are related to the young age of the patients, to the anatomical changes affecting the periarticular tissues, to the presence of hardware and to the greater exposure to septic complications. All these factors may prevent the surgeon to achieve a good cup positioning and a satisfying outcome. However a correct surgical technique, associated with meticulous pre-operative planning and the use of low-wear implants can improve the clinical result and the long term survival rates.

However, the literature about mid-to-long-term studies about post-traumatic THAs is scarce (currently 5 with an average follow-up of at least 5 years). Furthermore, these studies often include outdated implants, positioned with invasive surgical techniques and with removal of all previous hardware. Therefore, a long-term study (minimum 10-year follow-up) involving more recent implants, with modern articular couplings demonstrating low wear (such as ceramic-on-ceramic), and performed with minimally invasive technique and pre-operative CT-guided planning, would be desirable.

The aim of this study is to describe the survival rates and the long-term clinical and radiological outcome (minimum 10-year follow-up) of cementless THAs, with ceramic-on-ceramic couplings, performed with minimally-invasive technique and CT guided pre-operative planning, in post-traumatic osteoarthritis due to acetabular fractures

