### **Population**

retrospective, consecutive population treated with a cementless total hip arthroplasty with ceramic-on-ceramic bearing surfaces for post-traumatic hip osteoarthritis due to acetabular fracture. A minimum follow-up of 10 years was mandatory

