#### Inclusion criteria

- symptomatic, post-traumatic hip osteoarthritis due to acetabular fracture
- consecutive population with a minimum follow-up of 10 years
- cementless total hip arthroplasty with ceramic-on-ceramic bearing surfaces
- pre-operative planning using CT
- complete clinical and radiographic assessment

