#### Exclusion Criteria:

- other type of hip osteoarthritis
- other type of implants
- inadequate pre-operative planning (eg: no CT)
- incomplete assessment

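### Does naming minimally invasive technique in the aim, but not in the eligibility criteria, leave the analysed cohort unclear?

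*Combined protocol and SAP*

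**What the plan says.** The document states its aim twice. The Brief summary gives it as to "evaluate the long-term clinical and radiographic results of this implant in such a specific cohort", having just identified the implant (cementless, ceramic-on-ceramic) and the indication (osteoarthritis after acetabular fracture). The Study description gives a longer form, for arthroplasties "performed with minimally-invasive technique and CT guided pre-operative planning, in post-traumatic osteoarthritis due to acetabular fractures". Its preceding paragraph explains why: earlier studies often used outdated implants, "positioned with invasive surgical techniques and with removal of all previous hardware", so a long-term study of newer implants "and performed with minimally invasive technique and pre-operative CT-guided planning, would be desirable".

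The Population section describes a "consecutive population treated with a cementless total hip arthroplasty with ceramic-on-ceramic bearing surfaces for post-traumatic hip osteoarthritis due to acetabular fracture", with at least 10 years of follow-up. The Inclusion criteria add "pre-operative planning using CT" and complete assessment. The Exclusion Criteria mirror this by removing other types of osteoarthritis, other implants, "inadequate pre-operative planning (eg: no CT") and incomplete assessment. None of these sections mentions how invasive the surgery was.

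**The concern.** Two procedural features stand side by side in the longer aim. CT planning became both an inclusion and an exclusion criterion, while minimally invasive technique became neither and has no definition. Read literally, a hip operated on through another exposure would meet every eligibility criterion yet fall outside the aim.

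The label also does some work in the rationale. The Study description counts invasive technique among three limitations of earlier studies and says that sound technique, with planning and low-wear implants, can improve results. It also quotes 10-year revision rates of 15% to 26% from earlier reports, which readers may set beside this cohort's survival curve. If the results were presented as those of a minimally invasive series and some hips were not done that way, the description of the cohort would be wrong.

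**Working it through.** No arithmetic applies: the plan states no figure that depends on technique, and it gives neither the share of hips by exposure nor any effect of exposure on revision. The check is a comparison of the sections.

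| Section | Indication | Cementless, ceramic-on-ceramic | CT planning | Minimally invasive technique |
|---|---|---|---|---|
| Brief summary (aim) | yes | yes | no | no |
| Study description (aim) | yes | yes | yes | yes |
| Population | yes | yes | no | no |
| Inclusion criteria | yes | yes | yes | no |
| Exclusion Criteria | yes, by excluding other osteoarthritis | only as other implants excluded | yes, by excluding inadequate planning | no |

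**1. Is there a contradiction?** No. The sections differ in detail, and none says that another technique was used or permitted. The Brief summary and Population also leave out CT planning, which the eligibility lists then require. Silence in those two places is therefore weak evidence that a different cohort was meant. The only real asymmetry is between the longer aim and the eligibility lists.

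**2. Which text fixes the analysed set?** The Population section and the eligibility lists. They give a consecutive series by indication, implant, bearing, CT planning, follow-up and complete assessment. An analyst selecting hips from these criteria would apply no filter on technique.

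**3. Does technique enter any analysis?** The Methods use the HHS and WOMAC scores, a radiographic rule for the cup (at least 3 of 5 parameters) and Kaplan-Meier survival. The Statistical analysis plan defines failure as revision of any one component. Its chi-squared, Fisher and t tests are described in general terms, and no grouping by technique is named. Technique is an input to none of these.

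**4. What follows in each possible case?**

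- Every eligible hip was done with the technique. The aim and the cohort then coincide, and the phrase is a correct description.
- Some eligible hips were not. They are still eligible and still analysed. The scores, radiographic results and survival curve are unchanged, and only the descriptive phrase is too narrow.

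The analysed hips and the estimates are the same in both cases.

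**The case for a change.** The strongest opposing argument is that in a descriptive study the label of the cohort is much of what the results mean. Technique is part of the stated reason for doing the study, yet nothing in the plan defines, requires or records it. Brevity does not excuse this, because the full eligibility lists omit it while keeping its neighbour, CT planning. The nearest thing to a definition is the contrast with earlier studies. That contrast lists technique and hardware removal separately, so it is unclear whether leaving hardware in place is part of the meaning. The repair would be cheap: one sentence of aim, or a definition and one variable per hip.

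The textual observation stands in full: the term is undefined and has no counterpart in eligibility. The inference that the subject of the results is uncertain does not. Eligibility settles that they describe all eligible hips, and the open question is only whether one adjective fits every one of them. Nor does the plan use technique to explain any result. A comparison with the quoted 15% to 26% could not be credited to technique in any event, since by the document's own account earlier studies also differed in implants and hardware removal. The cheap repair would tidy the text without altering an estimate, and collecting a new variable from records at least 10 years old might not classify every hip.

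**Conclusion.** No change to the plan follows. The longer aim carries a descriptive phrase that the eligibility criteria do not repeat. This is a wording inconsistency with no shown effect on any result. Followed as written, the plan analyses a cohort that is defined without the phrase, and its results are as sound as they would be had the phrase been aligned.

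The conclusion rests on two readings of the text: that the Population section and eligibility lists determine who is analysed, and that no comparison by technique is intended. It would not hold if the study set out to compare exposures or to attribute survival to technique; a definition and a recorded variable would then be needed. For the report, ordinary good practice is enough: describe the surgery as the records show it, and call the series minimally invasive only if they support that.

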### **Population**

retrospective, consecutive population treated with a cementless total hip arthroplasty with ceramic-on-ceramic bearing surfaces for post-traumatic hip osteoarthritis due to acetabular fracture. A minimum follow-up of 10 years was mandatory

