### Methods

Clinical patient evaluation was assessed by using the HHS and WOMAC score at the minimum follow-up of 10 years.

Radiological evaluation was assessed using Moore's criteria regarding osseointegration (radial trabeculae, superior and inferior buttresses, stress shielding, absence of radiolucent lines). Adequate osseointegration of the cup: at least 3 parameters out of 5.

A prosthetic implants survival rate evaluation has been made using Kaplan-Meier method.

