### Statistical analysis plan

Statistical analysis has been done by using Windows SPSS 14.0, 14.0.1 version (SPSS Inc, Chicago, IL) and JMP, 12.0.1 version (SAS Institute Inc, Cary, NC, 1989-2007).

The quantitative data were expressed as average values and standard deviations, adding the range of minimum and maximum values. Statistical analysis was realized using Chi-squared test or Fisher exact test for qualitative data. Comparison of averages was performed using Student T test (significant correlation  $P<.05$ ).

The survival curves have been calculated and plotted according to Kaplan-Meier method. On x-axis time is expressed in years, while on y-axis the percentage of prosthesis survival is reported. The curve starts by definition at 100% survival when the period of follow-up begins. The implant is considered to be "surviving" up to when it was necessary to replace even single component. End point is the prosthesis failure. Prosthesis failure is defined as the revision of even one prosthetic component.

Each curve is flanked by a pair of curves symmetrical to it that are the 95% Confidence Interval. The range of the interval is closely dependent on the number of operations considered in the analysis. When the number of operations is low, uncertainty of analysis is high and showed by a wide confidence interval.

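### Entry to the only cohort depends on events after surgery and no censoring rule is given, so the survival and failure rates can be biased in either direction

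*Combined protocol and SAP*

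**What the plan says.** All references are to the combined protocol and SAP.

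- **Population:** "A minimum follow-up of 10 years was mandatory".
- **Inclusion criteria:** the 10-year condition is repeated as "consecutive population with a minimum follow-up of 10 years", and entry also needs "complete clinical and radiographic assessment".
- **Exclusion Criteria:** "incomplete assessment" removes a patient.
- **Methods:** "Clinical patient evaluation was assessed by using the HHS and WOMAC score at the minimum follow-up of 10 years". The clinical part of a complete assessment is therefore not available until year 10.
- **Statistical analysis plan:** survival is by Kaplan-Meier. "The curve starts by definition at 100% survival when the period of follow-up begins", and "Prosthesis failure is defined as the revision of even one prosthetic component".
- **Brief summary:** "The secondary aim of the study is to provide the complication rate and the failure rate of the cohort". A description of the failures is also promised. The Study description names survival rates among the aims.

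No section says what happens to a patient who dies or is lost before 10 years, or whether a hip revised before 10 years meets the entry criteria. There is no censoring rule, and the failure and complication rates have no stated denominator.

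**The concern.** Kaplan-Meier is designed to use hips with incomplete follow-up: each counts as at risk until it fails or is last seen. Here the entry rule can remove those hips before the curve is drawn, although the clock starts well before the entry condition can be met. Whether a hip is in the analysis then depends on its later course.

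The direction of the error depends on a rule that the plan does not state. Keeping revised hips while dropping unrevised deaths and losses inflates the failure rate. Dropping revised hips, or losing them more often, deflates it. There is no control arm in which the error could cancel, and readers will set the result beside the protocol's background 10-year revision rate of 15-26%. The series is called consecutive, but these filters can turn it into an unknown subset of the hips operated on.

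**Working it through.** The plan gives no sample size, event count or survival estimate, so there is no figure of its own to reproduce. The calculation below shows how far the entry rule alone can move the result.

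**Inputs.**
- True 10-year revision rate R: 15% and 26% from the Study description, with 20% as an assumed value between them.
- Death or loss by 10 years, D: 20% assumed, range 10-30%. The documents give no figure.
- Constant hazards: a = -ln(1-R)/10 for revision and b = -ln(1-D)/10 for death or loss. Loss before revision is independent of revision.

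In readings 2 and 3 every retained hip is either revised or followed to 10 years, so the Kaplan-Meier estimate at 10 years equals the simple proportion revised.

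**Reading 1: follow-up means time since surgery and nobody is dropped.** No selection and no bias.

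**Reading 2: observed revisions are kept; unrevised deaths and losses are dropped.**
- Revisions observed by 10 years: rev = a/(a+b) × (1 - exp(-10(a+b))).
- Unrevised and seen at 10 years: (1-R)(1-D).
- Apparent rate = rev / (rev + (1-R)(1-D)).

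With R = D = 20%, a = b = 0.02231. Then rev = ½ × (1 - 0.64) = 0.18, the unrevised share is 0.8 × 0.8 = 0.64, and the apparent rate is 0.18/0.82 = 22.0%.

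| True rate | D = 10% | D = 20% | D = 30% |
|---|---|---|---|
| 15% | 15.7% | 16.5% | 17.6% |
| 20% | 20.9% | 22.0% | 23.2% |
| 26% | 27.1% | 28.4% | 29.9% |

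A separate simulation of 400,000 hips per scenario gave 15.7%, 16.6% and 17.5% for a true 15%, and 27.0%, 28.4% and 29.7% for a true 26%.

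**Reading 3: every hip, revised or not, must be assessed at 10 years.** Let the loss hazard after revision be m times b.
- seen = ∫₀¹⁰ a·exp(-(a+b)t)·exp(-m·b·(10-t)) dt.
- Apparent rate = seen / (seen + (1-R)(1-D)).

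With R = D = 20%:
- m = 1: seen = 0.2 × 0.8 = 0.16, and 0.16/0.80 = 20.0%. No bias.
- m = 2: the terms in t cancel, so seen = 10a × 0.64 = 0.2231 × 0.64 = 0.1428, and 0.1428/0.7828 = 18.2%.
- m = 3: seen = 0.512 × 0.25 = 0.128, and 0.128/0.768 = 16.7%.
- m = 0.5: seen = 0.1696, and 0.1696/0.8096 = 21.0%.

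For R = 20%, the same formula at D = 10% gives 19.1% (m = 2) and 18.3% (m = 3). At D = 30% it gives 17.3% and 15.0%. For m = 0.5 the range over D is 20.4-21.5%.

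**Reading 4: early revisions fail the entry rule.** If all are excluded, 10-year survival is 100% by construction. If 25-75% of them are kept and unrevised losses are dropped, simulation gave 4.4-13.8% for a true 15% and 8.5-24.1% for a true 26%.

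**Hips removed.** At R = 20%, reading 2 keeps 0.910, 0.820 and 0.729 of hips at D = 10%, 20% and 30%. Reading 3 with m = 1 to 3 keeps between 0.900 and 0.659. So 9-34% of the consecutive hips leave the denominator.

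**All hips, with censoring.** Kaplan-Meier on every simulated hip, censored at death or loss, returned 0.7999-0.8005 for a true survival of 0.80. It also recovered 0.85 and 0.74, to within 0.0006.

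**The case against.** The strongest reply is that the wording is ambiguous, which does not show that selection took place. Both statements of the 10-year minimum concern a consecutive population, which fits a plain administrative cut-off on the date of surgery. The promised failure rate and description of failures, together with an event defined as revision of any component, imply that revised hips stay in. The shifts are also modest. With 50-100 hips (an assumption, since no sample size is stated), a 20% rate has a 95% interval of about ±1.96 × √(0.2 × 0.8/n), or ±11 to ±8 points, wider than the shifts in readings 2 and 3. No formal test against 15-26% is planned. Finally, the recovery of the true value by censoring follows from simulating loss as independent of revision.

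Much of this stands as a limit on the claim. The sizes are illustrations, reading 4 in its extreme form is unlikely, and censoring at last contact would itself be biased if failing hips were preferentially lost before revision was recorded.

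It does not remove the problem. The benign reading needs two things: that follow-up means time since surgery, and that nobody is dropped for incomplete assessment. The Exclusion Criteria section contradicts the second. A promise to describe failures does not show that every early failure is retained. A wide confidence interval reflects sampling error and does not cover bias.

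**Conclusion.** The concern holds. As worded, one cohort is selected on 10 years of follow-up and a complete assessment, and is then used for a survival curve starting at 100%, with no censoring rule. For a true 10-year revision rate of 20% and 10-30% death or loss, the apparent rate runs from 15.0% (every hip must be assessed, loss three times higher after revision, 30% loss) to 23.2% (revisions kept, unrevised losses dropped, 30% loss). It is exactly 20% when loss is unrelated to revision and every hip faces the same assessment rule. Loss of part of the early revisions would push it lower still.

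These figures rest on constant hazards and on loss rates and multipliers that the documents do not supply. The conclusion that neither the size nor the direction of the bias can be determined from the plan does not depend on them. Because survival and failure rates are stated aims, this should be corrected before the rates are reported.

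**What to change.** 1. Define the survival cohort by facts known at surgery: every consecutive hip meeting the diagnosis, implant and pre-operative CT criteria and operated on at least 10 years before a stated cut-off date. The documents give a primary completion date of July 19, 2019 but name no data cut-off.
2. Start the clock at surgery, count revision of any component whenever it occurred, and censor unrevised hips at death or last contact. State that this assumes loss is unrelated to the risk of revision.
3. State that no hip leaves the survival, failure-rate or complication-rate analysis because of death, loss, early revision or incomplete assessment.
4. Apply the 10-year minimum and the completeness criteria only to the HHS, WOMAC and radiographic summaries.
5. Report how many hips were operated on, were revised before 10 years, died or were lost before 10 years, and were assessed at 10 years or later, with the number at risk at 10 years.

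The cost is wording changes in the Population, criteria and Statistical analysis plan sections, plus chart review for hips without a 10-year assessment. The survival figure may move in either direction, some hips will contribute shorter follow-up, and the clinical summaries will rest on fewer hips than the survival curve. If the administrative cut-off was what the sponsor meant, these changes simply put that in writing.

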#### Inclusion criteria

- symptomatic, post-traumatic hip osteoarthritis due to acetabular fracture
- consecutive population with a minimum follow-up of 10 years
- cementless total hip arthroplasty with ceramic-on-ceramic bearing surfaces
- pre-operative planning using CT
- complete clinical and radiographic assessment

#### Exclusion Criteria:

- other type of hip osteoarthritis
- other type of implants
- inadequate pre-operative planning (eg: no CT)
- incomplete assessment

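### Requiring complete clinical and radiographic assessment for entry can remove hips from the failure and complication rates, and no count of those removed is planned

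*Combined protocol and SAP*

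**What the plan says.** - **Entry.** The Inclusion criteria list "complete clinical and radiographic assessment", and the Exclusion Criteria list "incomplete assessment". Neither names an outcome or a time point. Both apply to the only cohort the document describes.
- **Population.** It is described as a "retrospective, consecutive population treated with a cementless total hip arthroplasty", and separately "A minimum follow-up of 10 years was mandatory".
- **Aims.** The Brief summary promises, as a secondary aim, complication and failure rates for the cohort, together with a description of the failures. The Study description also names survival as an aim.
- **Measurements.** Under Methods, "Clinical patient evaluation was assessed by using the HHS and WOMAC score at the minimum follow-up of 10 years". Osseointegration is judged on films by Moore's criteria, and no date is given for the films.
- **Failure.** In the Statistical analysis plan, "Prosthesis failure is defined as the revision of even one prosthetic component".
- **Precision.** The same section says of the confidence interval: "The range of the interval is closely dependent on the number of operations considered in the analysis".

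The document does not define a complete assessment, and it does not say whether a hip revised before year 10 counts as completely assessed. It names no separate population for survival or complications, gives no missing-data rule, and does not provide for a count of hips excluded as incomplete.

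**The concern.** A hip score and an osseointegration reading are needed to report function and fixation. They are not needed to know whether and when a component was revised. Kaplan-Meier estimation handles unequal follow-up by censoring, so it does not need complete clinical and film data either. Making completeness an entry condition lets a gap in one measurement remove the hip from every outcome.

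The series is presented as consecutive, and readers will take its failure rate as that of consecutive hips. The rule can turn it into a complete-case subset. If revised hips are less often fully assessed, the reported failure rate is too low; if they are more often fully assessed, it is too high. Without a count of excluded hips and their known status, a reader cannot tell whether either has happened. Even without bias, hips that could contribute are lost and the interval widens.

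The same reasoning reaches any complication that can be recorded without a score or a late film. The document does not list its own complications. Of the types in its background section, dislocation, infection and neurovascular lesion appear to qualify, which is an inference. Ossification does not, because it is read on films.

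**Working it through.** The plan gives no sample size, event count or number excluded, so it has no figure to reproduce. The calculations below show how sensitive the reported rates are.

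**Scope.** Only hips that already meet the 10-year rule are considered, so 10-year failure is treated as a simple proportion. This presupposes that follow-up continues after a revision; the document does not say.

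**Inputs.** The Study description gives a background 10-year revision rate of 15% to 26%, dislocation 4.4%, infection 5.6% and neurovascular lesion 2.1%. All excluded shares and completeness shares, and the true failure rate of 20%, are assumptions.

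**1. Bound.** Let a share m be excluded as incomplete and let f be the reported failure rate in the rest. The rate in all of them is lowest if no excluded hip failed, f(1 − m), and highest if every one did, f(1 − m) + m. With f = 15%:

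| m | Lowest | Highest |
|---|---|---|
| 0% | 15.0% | 15.0% |
| 5% | 0.15 × 0.95 = 14.25% | 14.25% + 5% = 19.25% |
| 10% | 0.15 × 0.90 = 13.5% | 13.5% + 10% = 23.5% |
| 20% | 0.15 × 0.80 = 12.0% | 12.0% + 20% = 32.0% |

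The width always equals m.

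**2. Unequal completeness.** Let R be the true rate, p1 the share complete among hips without the event and p2 the share among hips with it. The apparent rate is R·p2 / [R·p2 + (1 − R)·p1], and the share excluded is one minus the denominator. With R = 20%:

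| p1 | p2 | Apparent rate | Excluded |
|---|---|---|---|
| 90% | 60% | 0.12 / (0.12 + 0.72) = 14.3% | 16% |
| 70% | 90% | 0.18 / (0.18 + 0.56) = 24.3% | 26% |
| 90% | 90% | 0.18 / (0.18 + 0.72) = 20.0% | 10% |

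**3. Complications.** The same formula, with the background rates taken as true:

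| Complication | True | p1 = 90%, p2 = 60% | p1 = 70%, p2 = 90% |
|---|---|---|---|
| Dislocation | 4.4% | 0.0264 / 0.8868 = 3.0% | 0.0396 / 0.7088 = 5.6% |
| Infection | 5.6% | 0.0336 / 0.8832 = 3.8% | 0.0504 / 0.7112 = 7.1% |
| Neurovascular lesion | 2.1% | 0.0126 / 0.8937 = 1.4% | 0.0189 / 0.7042 = 2.7% |

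From the denominators, the first pattern excludes about 11% to 12% of hips and the second about 29% to 30%.

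**4. Precision without bias.** At an unchanged rate, interval width is roughly proportional to 1/√n, so excluding a share m multiplies it by 1/√(1 − m). For m = 10% this is 1/√0.90 = 1.054, and for m = 20% it is 1/√0.80 = 1.118: about 5% and 12% wider.

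**The case against.** The strongest reply is that the rule may have little effect of its own. The scores are tied to follow-up of at least 10 years, and that follow-up is already mandatory. If reaching it means attending the assessment, the completeness rule removes few further hips, mainly those lacking a film, and the 10-year rule is the larger restriction on a consecutive series. This stands as a caution: changing the completeness rule alone does not restore the whole series.

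A second reply concerns the figures. The completeness pairs have no anchor in the document, and some imply heavy exclusion. The upper bound requires every excluded hip to have failed, which is a worst case and not a likely bias. If follow-up instead ended at revision, a hip revised before year 10 would fail the 10-year rule and no early failures would remain among the hips considered, so a reported 15% could not arise. All of this is fair and limits the figures to illustration.

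Third, both criteria follow directly after the CT planning criteria, so completeness might mean the pre-operative work-up, with a smaller effect. The document does not exclude this reading. However, CT planning has its own criterion, and the rule would still govern the whole cohort.

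Finally, clinical and radiographic results are the leading aim, and requiring the measurements serves it. That justifies the requirement for those outcomes. It does not justify it for revision, which the plan defines without them. A count may yet appear in the report, but the plan does not ask for one.

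**Conclusion.** The concern holds. Followed as written, the eligibility rule can remove hips with known revision or complication status from rates that do not need the missing measurement, and the plan neither restores nor counts them. Confidence is high for that reading.

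The size of any bias is unknown, its direction is not fixed, and it is zero if no hip is excluded or if completeness is unrelated to the event. Modest exclusion is enough to matter: 10% excluded leaves a 10-point range around a reported 15%, and the assumed completeness patterns move a true 20% to 14.3% or 24.3%. The complication part also rests on the inference about which complications need no score or film. The change should be made, because failure and complication rates are a stated aim and survival is named as one too.

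**What to change.** - Delete both completeness criteria from eligibility and apply completeness separately for each outcome.
- Keep every otherwise eligible hip in the Kaplan-Meier analysis up to its last known implant status, in the rates of complications that need no film, and in the description of failures. Do not count unknown status as event-free.
- Summarise HHS, WOMAC, osseointegration and film-based complications in the hips that have the measurement.
- Define for each outcome what a complete measurement is, including for hips revised before year 10.
- Report for each outcome the number of hips missing, with their known revision and complication status.

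The cost is a change of eligibility wording, some extra record extraction and one table of missing data. Denominators will differ between outcomes, and the rates may look less favourable. Hips removed by the 10-year follow-up rule are not recovered by this change.
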